- 222 Female subject of childbearing potential or male subject of reproductive potential who is unwilling to use acceptable method(s) of effective contraception during study treatment and through 3 months after the last dose of talimogene laherparepvec/placebo or 4 months after the last dose of pembrolizumab, whichever is later. Note: Women not of childbearing potential are defined as:
- Postmenopausal (defined as at least 12 months with no menses without an alternative medical cause; in women < 45 years of age a high follicle stimulating hormone [FSH] level in the postmenopausal range may be used to confirm a postmenopausal state in women not using hormonal contraception or hormonal replacement therapy. In the absence of 12 months of amenorrhea, a single FSH measurement is insufficient)
- OR
- Have had a hysterectomy and/or bilateral oophorectomy, or bilateral salpingectomy at least 6 weeks prior to screening
- OR
- Has a congenital or acquired condition that prevents childbearing
- For this trial, male subjects will be considered to be of non-reproductive potential if they have azoospermia (whether due to having had a vasectomy or due to an underlying medical condition). Note: Acceptable methods of effective contraception are defined in the informed consent form. Additional country-specific contraception requirements may be defined in a country-specific protocol supplement at the end of the Appendix Section of the protocol as required by local laws and regulations.
- If there is any question that a subject of reproductive potential will not reliably comply with the requirements for contraception, that subject should not be enrolled into the study.
- 223 Sexually active subjects or their partners unwilling to use male or female latex condom to avoid potential viral transmission during sexual contact while on treatment and within 30 days after treatment with talimogene laherparepvec/placebo. **For those with latex allergies, polyurethane condoms may be used.**
- 224 Subject has known sensitivity to any of the products or components to be administered during study treatment.

- 225 Subject likely to not be available to complete all protocol-required study visits or procedures, and/or to comply with all required study procedures to the best of the subject and investigator's knowledge.

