The maximum volume of talimogene laherparepvec/placebo administered at any dose is 4.0 mL for any individual tumor lesion. The maximum volume at any treatment visit is 8.0 mL. Investigators are encouraged to use the maximum volume whenever lesions allow. The recommended volume of talimogene laherparepvec/placebo to be injected into the tumor(s) is dependent on the size of the tumor(s) and should be determined according to the injection volume guideline in [Table 2](#).

Table 2. Talimogene Laherparepvec Injection Volume Guideline Based on Tumor Size

Tumor Size (longest dimension)	Maximum Injection Volume
> 5.0 cm (50 mm)	4.0 mL
> 2.5 cm (25 mm) to 5.0 cm (50 mm)	2.0 mL
> 1.5 cm (15 mm) to 2.5 cm (25 mm)	1.0 mL
> 0.5 cm (5 mm) to 1.5 cm (15 mm)	0.5 mL
\leq 0.5 cm (5 mm)	0.1 mL

On each treatment day, prioritization of injections is recommended as follows:

- any new injectable tumor that has appeared since the last injection
- by tumor size, beginning with the largest tumor
- any previously uninjectable tumor(s) that is now injectable

It is recommended that each lesion should receive the maximum amount possible to inject due to tumor properties at each visit before moving on the next lesion, using the prioritization model above and the injection volume guideline based on tumor size per [Table 2](#). Tumor measurements for injection volume determination may be done by caliper measurements and/or by ultrasound guided measurements. Most recent prior radiographic tumor assessment measurements may be used to determine injection volume if caliper measurements and/or ultrasound guided measurements are not feasible and/or unavailable. The lesions injected will be recorded on the CRF.

Note: Continued injection into nodal lesions that have decreased to < 10 mm is up to the discretion of the investigator.

Subjects will be treated with talimogene laherparepvec/placebo until subjects have achieved a iCR, no injectable lesions, confirmed iPD (response per irRECIST), intolerance of study treatment, 24 months from the date of the first dose of talimogene laherparepvec/placebo, or end of study, whichever occurs first. Due to the mechanism of action, subjects may experience growth in existing tumors or the appearance of new tumors prior to maximal clinical benefit of study therapy. The dose, start date, and lot number of talimogene laherparepvec/placebo are to be recorded on each subject's CRF.

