- The subject, for any reason, requires treatment with another anticancer therapeutic agent for treatment of the study disease (other than the exceptions noted in Excluded Treatments and/or Procedures During Study Period [[Section 6.9](#)]). In this case, discontinuation from the treatment occurs immediately upon introduction of the new agent.
- Confirmed iPD occurs as defined per the irRECIST ([Appendix D](#)).
- A grade 2 or greater immune-mediated adverse event (with the exception of vitiligo) or allergic reactions attributed to talimogene laherparepvec/placebo that would require a dose delay of greater than 4 weeks from the date of the planned dose.
- Note: immune-mediated glomerulonephritis, vasculitis, and pneumonitis and exacerbation of psoriasis have been observed in subjects receiving talimogene laherparepvec in clinical trials. Most of these subjects had a history of other autoimmune disease and/or prior treatment with agents that offered plausible alternative etiologies however, immune-mediated adverse events can potentially involve any organ system.
- Any other talimogene laherparepvec/placebo-related non-hematologic or hematologic toxicities grade 3 or greater occur that, in the opinion of the investigator, would require a dose delay of greater than 4 weeks from the date of the planned dose.
- The subject develops clinical evidence of any systemic herpes infection (such as encephalitis or disseminated infection).
- A female subject becomes pregnant or fails to use acceptable method(s) of effective contraception (for those subjects who are able to conceive).
- A female subject breast feeds while on study treatment.
- Concurrent medical illness that, in the judgment of the investigator, would make continued treatment with talimogene laherparepvec/placebo dangerous for the subject.

For additional information, related special warnings, and precautions for the use of talimogene laherparepvec/placebo please refer to the latest version of the talimogene laherparepvec [Investigator's Brochure](#).

In the event talimogene laherparepvec/placebo is delayed or permanently discontinued for talimogene laherparepvec/placebo-related toxicity, pembrolizumab may continue to be administered, as long as the toxicity is clearly not related to pembrolizumab. Likewise in the event pembrolizumab is delayed or permanently discontinued for pembrolizumab-related toxicity, talimogene laherparepvec/placebo may continue to be

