Week	Study Treatment ^a													Follow-up Period
	0	0	0	1	2	3	3	3	4	5	6	7	9	Safety Follow-up
Talimogene Laherparepvec Cycle	1	1	1	1	1	2	2	2	2	2	3	3	4	Day 30 Safety Follow-up Visit
Day	1	2	3	8	15	1	2	3	8	15	1	8	1	30 (+ 7) days after end of treatment
Blood ^a	X	X	X	X	X	X	X	X	X	X	X	X	X	X
Urine ^a	X	X	X	X	X	X	X	X	X	X	X	X	X	X
Swab of Surface of Exterior of Occlusive Dressing ^b		X	X	X	(X)	(X)	X	X	X	(X)	(X)	X	(X)	(X)
Swab of Surface of Injected Lesion ^b		X	X	X	X	X	X	X	X	X	X	X	X	X
Swab of Oral Mucosa ^c	X	X	X	X	X	X	X	X	X	X	X	X	X	X

^a Blood and urine sample for real-time polymerase chain reaction (qPCR) testing of talimogene laherparepvec DNA will be performed at the following time points: Cycle 1: day 1 (prior to and approximately 1 hour [\pm 15 minutes], 4 hours [\pm 30 minutes], after talimogene laherparepvec administration), day 2 (24 [\pm 4] hours after talimogene laherparepvec administration), day 3 (48 [\pm 4] hours after talimogene laherparepvec administration), day 8 (\pm 2 days), and day 15 (\pm 2 days). Cycle 2: day 1 (prior to and approximately 1 hour [\pm 15 minutes], 4 hours [\pm 30 minutes], after talimogene laherparepvec administration), day 2 (24 [\pm 4] hours after talimogene laherparepvec administration), day 3 (48 [\pm 4] hours after talimogene laherparepvec administration), and day 8 (\pm 2 days), and day 15 (\pm 2 days). Cycle 3: day 1 (prior to talimogene laherparepvec administration) and day 8 (\pm 2 days). Cycle 4: day 1 (prior to talimogene laherparepvec administration). Blood and urine samples for qPCR testing will also be collected at the 30-day safety follow-up visit (+7 days). Please refer to the Central Laboratory Manual for instructions regarding sample collection, storage, and shipment procedures.

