Cycle 1: day 2 (24 [± 4] hours after talimogene laherparepvec administration), day 3 (48 [± 4] hours after talimogene laherparepvec administration), day 8 (± 2 days) and day 15 (± 2 days). Cycle 2: day 1 (prior to talimogene laherparepvec administration), day 2 (24 [± 4] hours after talimogene laherparepvec administration), day 3 (48 [± 4] hours after talimogene laherparepvec administration), day 8 (± 2 days) and day 15 (± 2 days). Cycle 3: day 1 (prior to talimogene laherparepvec administration) and day 8 (± 2 days). Cycle 4: day 1 (prior to talimogene laherparepvec administration). During safety follow-up: Swabs of the surface of the injected lesion(s) (if a lesion is in complete response [CR], the place of the prior injection will be swabbed) will also be collected at the 30-day safety follow-up visit (+7 days). At each time point only if qPCR of talimogene laherparepvec DNA testing is positive, then a TCID50 assay will be performed to evaluate whether the presence of infective talimogene laherparepvec virus is detectable in the sample. Please refer to the Central Laboratory Manual for instructions regarding sample collection, storage, and shipment procedures.

^c Swabs of oral mucosa for qPCR of talimogene laherparepvec DNA testing and TCID50 assay will be collected at the following timepoints: Cycle 1: day 1 (prior to talimogene laherparepvec administration), day 2 (24 [± 4] hours after talimogene laherparepvec administration), day 3 (48 [± 4] hours after talimogene laherparepvec administration), day 8 (± 2 days), and day 15 (± 2 days). Cycle 2: day 1 (prior to talimogene laherparepvec administration), day 2 (24 [± 4] hours after talimogene laherparepvec administration), day 3 (48 [± 4] hours after talimogene laherparepvec administration), day 8 (± 2 days) and day 15 (± 2 days). Cycle 3: day 1 (prior to talimogene laherparepvec administration) and day 8 (± 2 days). Cycle 4: day 1 (prior to talimogene laherparepvec administration). If qPCR testing of talimogene laherparepvec DNA is positive, then a TCID50 assay will be performed to evaluate whether the talimogene laherparepvec virus is detectable in the sample. During safety follow-up: swab of oral mucosa for qPCR testing will be collected at the 30 day safety follow-up visit (+ 7 days). Please refer to the Central Laboratory Manual for instructions regarding sample collection, storage, and shipment procedures.

Table 7. Schedule of Assessments for Phase 3

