9.2 Safety Event Reporting Procedures

9.2.1 Reporting Procedures for Disease Related Events

The investigator is responsible for ensuring that all Disease Related Events (serious or non-serious) observed by the investigator or reported by the subject that occur after the first dose of talimogene laherparepvec/placebo or pembrolizumab through the safety follow-up visit (ie, 30 [+7] days after the last dose of talimogene laherparepvec/placebo or pembrolizumab, whichever is later), are recorded on the Event CRF as a Disease Related Event.

The investigator must assign the following attributes to each disease related event:

- disease related event diagnosis or syndrome(s), if known (if not known, signs or symptoms),
- dates of onset and resolution (if resolved)
- severity (and/or toxicity per protocol),
- assessment of relatedness to talimogene laherparepvec/placebo and/or pembrolizumab and,
- action taken

CTCAE version 4.0 will be used to grade a disease related event. The grading scale used in this study is described in [Appendix A](#).

Note: If the event is more severe than expected for the subject's condition or if the investigator believes there is a causal relationship between the investigational product(s)/study treatment/protocol required therapies and disease worsening, the event should be reported as an adverse event, not a disease related event.

The investigator is expected to follow reported disease related events (serious or non-serious) until stabilization or reversibility.

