10.6.8.2 Incidence of Clearance of Talimogene Laherparepvec DNA From Blood and Urine

Phase 1b

The number and proportion of subjects with undetectable talimogene laherparepvec DNA per qPCR among subjects with sample collected in each cycle will be presented. Incidence of clearance of talimogene laherparepvec DNA from Cycle 1, 2, 3, and 4 will

be calculated by cycle. An exact 95% CI for the binomial proportion will be calculated ([Clopper & Pearson, 1934](#)).

Analysis of incidence of clearance of talimogene laherparepvec DNA from blood and urine will be analyzed using the qPCR Blood Clearance Analysis Set and qPCR Urine Clearance Analysis Set, respectively.

10.6.8.3 Rate of Detection and Subject Incidence of Talimogene laherparepvec DNA and Virus From Blood, Urine, Exterior of Occlusive Dressing, Surface of Injected Lesions, and Oral Mucosa

Phase 1b

Rate of detection and subject incidence of talimogene laherparepvec DNA and virus will be analyzed separately for blood, urine, exterior of occlusive dressing, surface of injected lesions, and oral mucosa using qPCR Blood Analysis Set, qPCR Urine Analysis Set, qPCR Exterior Occlusive Dressing Analysis Set, qPCR Injected Lesion Analysis Set, and qPCR Oral Mucosa Analysis Set, respectively.

The number and proportion of subjects who have at least 1 positive qPCR result will be presented. The number and proportion of subjects exhibiting detectable virus from TCID50 assay will also be presented. Numeric results of positive qPCR, and separately for detectable virus from TCID50, will be summarized as a continuous variable. An exact 95% CI for the binomial proportion will be calculated ([Clopper & Pearson, 1934](#)).

Subject incidence and rate of subsequent positive TCID50 testing for positive qPCR testing results will be presented using qPCR Exterior Occlusive Dressing Analysis Set, qPCR Injected Lesion Analysis Set, and qPCR Oral Mucosa Analysis Set.

qPCR and TCID50 results for subjects having a positive qPCR testing will be reviewed.

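### The final shedding and biodistribution samples are timed from the last dose of either drug, so in subjects who stop talimogene laherparepvec first they do not describe shedding near 30 days after the last virus dose

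*Protocol*

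**What the plan says.** Table 6 (Protocol 7.1) schedules phase 1b blood, urine and swab samples over talimogene laherparepvec cycles 1 to 4. The last on-treatment sample is at week 9, before the cycle 4 injection. One further set sits in the follow-up column, timed "30 (+ 7) days after end of treatment". Footnote a says of blood and urine: "Blood and urine samples for qPCR testing will also be collected at the 30-day safety follow-up visit (+7 days". Footnote c says of the mouth: "swab of oral mucosa for qPCR testing will be collected at the 30 day safety follow-up visit (+ 7 days". Footnote b puts the injected-lesion swab at the same visit, and also the dressing swab if the lesion still needs a dressing.

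Protocol 9.2.1 gives the date of that visit: "30 [+7] days after the last dose of talimogene laherparepvec/placebo or pembrolizumab, whichever is later". SAP Section 6 ties it to the last dose of IP and defines IP as both products.

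The two drugs stop on different grounds. For talimogene laherparepvec, Protocol 6.2.1.1 lists "no injectable lesions, confirmed iPD (response per irRECIST), intolerance of study treatment" among the reasons. The first of these is not in the pembrolizumab list in 6.2.2.1, which allows treatment for up to 24 months. If talimogene laherparepvec is stopped for its own toxicity, 6.2.1.2 says "pembrolizumab may continue to be administered, as long as the toxicity is clearly not related to pembrolizumab".

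SAP 10.6.8.2 reports clearance from blood and urine separately for cycles 1 to 4. The analysis sets in SAP 7.12 and 7.13 need a positive sample followed by an evaluable one within the same cycle. For detection, SAP 10.6.8.3 states: "The number and proportion of subjects who have at least 1 positive qPCR result will be presented". Neither section tabulates results by time since the last injection.

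**The concern.** What matters for a post-treatment shedding sample is the time since virus was last injected. Here the clock starts at the last dose of whichever drug ran longer. In a subject who stops injections and stays on pembrolizumab, the sample labelled Day 30 can be taken months after the last virus dose. A negative result then says little about shedding at 30 days.

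Elsewhere the protocol counts from the virus dose. Exclusion criterion 223 sets condom use "within 30 days after treatment with talimogene laherparepvec/placebo", criterion 228 uses the same interval for avoiding contact with people at higher risk, and section 9.4 monitors exposure of contacts for 30 (+7) days after the last injection. In the subjects who stop injections early, the post-treatment samples describe a different interval from the one these provisions use.

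**Working it through.** No sample size, power or stated figure is involved. The check is of dates.

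**Inputs.** Visit window 30 to 37 days after the later last dose (9.2.1). Dosing every 3 weeks for both drugs (6.2.1.1, 6.2.2.1). Pembrolizumab limit 24 months, or 24 × 30.4375 / 7 = 104.4 weeks, so the last 3-weekly dose inside it is week 102. Estimated median treatment period 7 months (3.5.1), or 30.4 weeks, so about week 30. That median is for study treatment as a whole, and the dose dates below are illustrative assumptions.

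**Formula.** Days from last virus dose to follow-up sample = 7 × (last pembrolizumab week − last virus week) + 30 to 37.

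| Last virus dose | Last pembrolizumab dose | Calculation | Follow-up sample, days after last virus dose |
|---|---|---|---|
| week 9 | week 9 | 0 + 30 to 37 | 30–37 |
| week 9 | week 12 | 21 + 30 to 37 | 51–58 (about 7–8 weeks) |
| week 9 | week 18 | 63 + 30 to 37 | 93–100 (about 3 months) |
| week 9 | week 30 | 147 + 30 to 37 | 177–184 (about 6 months) |
| week 9 | week 102 | 651 + 30 to 37 | 681–688 (about 22 months) |

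**What else is sampled after the last virus dose.**
- Last dose in cycle 4 or later: nothing before safety follow-up.
- Last dose in cycle 3: days 7 and 21 after it, the second being the cycle 4 day 1 sample.
- Last dose in cycle 1 or 2: if Table 6 is followed by calendar week, a blood and urine sample would still fall about 28 days after it. The footnotes index samples by talimogene laherparepvec cycle and do not say whether sampling continues once injections stop.
- Injected-lesion swab: footnote b repeats it on treatment only if the lesion is injected again, so a lesion no longer injected waits for safety follow-up.

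**Clearance by cycle.** Cycles 1, 2 and 3 each have samples after the injection within the cycle, so their estimates do not need the follow-up visit. Cycle 4 has a single sample, taken before the injection. A later sample counted in cycle 4 could only be the follow-up one.

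**Subject-level detection.** A subject counts as positive after any positive result. A late negative leaves the numerator unchanged. It also leaves the denominator unchanged for anyone with another evaluable post-dose sample.

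**If a sample-level rate were used.** The heading of SAP 10.6.8.3 mentions a rate of detection, but no sample-level denominator is defined. Blood has 7 + 7 + 2 + 1 + 1 = 18 scheduled samples per subject, 17 of them post-dose. If 10% to 40% of 40 subjects were affected (an assumption), 4 to 16 late samples out of 40 × 17 = 680 would be 0.6% to 2.4%, with every scheduled sample taken.

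**The case against.** The strongest reply is that the plan does not set out to measure clearance at 30 days. That is correct: neither document names such an endpoint, and SAP clearance is defined within cycle. A reader might infer that the trial fails to deliver a 30-day clearance result; the documents do not support that.

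Three other stronger readings also fail.
- Late negatives do not materially dilute the detection results. The proportion the SAP states is per subject, and even an undefined per-sample rate would move little.
- The follow-up set is not the only source on the 30 days after a dose. Day 8 and day 15 samples in cycles 1 and 2, day 8 in cycle 3, and the pre-dose samples of cycles 2 to 4 (about day 21) all fall inside it. The uncovered part is roughly day 22 onward.
- The contact precautions are not shown to depend on these samples. They already run from the last virus dose, and no section makes them conditional on shedding results. Suspected herpetic lesions are swabbed when they occur (7.4.2), and exposed contacts may be swabbed (9.4).

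It is also true that re-timing comes late. SAP Section 11 records that the phase 1b primary analysis has been reviewed and that phase 3 will not proceed, and Table 6 applies to phase 1b only.

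What stands is narrower. The anchor to the later drug is explicit, the drugs can stop apart, and nothing else covers the period after a cycle 4 or later injection. SAP Section 1 still covers the follow-up and final analyses, so the reporting can be changed.

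**Conclusion.** The point holds for subjects who stop talimogene laherparepvec before pembrolizumab. Their final sample set can fall from about 7 weeks to about 22 months after the last virus dose (last virus dose taken as week 9). It therefore does not describe shedding near 30 days. A late negative is not evidence of clearance by then, though a late positive would still show persistence. Any cycle 4 clearance estimate would rest on a sample of uncontrolled timing.

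Clearance in cycles 1 to 3, the subject-level detection proportions and subjects who stop both drugs together (sampled at days 30 to 37) are essentially unaffected. The number of subjects affected is unknown; 4 to 16 of 40 follows only from the assumed 10% to 40%. The endpoint is exploratory, and the DLT and efficacy conclusions are untouched. This is a worthwhile low-cost improvement.

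**What to change.** 1. **Table 6 and footnotes a to c.** Time the final set from the last talimogene laherparepvec dose. If pembrolizumab continues, collect the set at the first scheduled visit at least 30 days after that dose. One 3-weekly interval gives 21 ± 3 = day 18–24, which is too early; two give 42 ± 6 = day 36–48. If both drugs stop together, keep the safety follow-up visit.
2. **SAP 10.6.8.2 and 10.6.8.3.** Report the follow-up samples separately by actual days since the last talimogene laherparepvec dose, for example 30–37, 38–60 and more than 60 days. State that late negatives are not read as clearance by 30 days. Say whether a follow-up sample can count toward cycle 4 clearance and, if so, within what interval.

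The first change moves the same samples to an existing visit and changes sampling only. Its small downside is that some samples fall after day 37, and it helps only subjects not yet sampled. The second needs only recorded dose and sample dates and can be applied to the remaining analyses.
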